8 DEFINITIONS AND CONVENTIONS FOR DATA HANDLING

The data will be handled as follows. The sponsor will determine how to handle all data prior to data base lock.

8.1 PHARMACOKINETIC DATA HANDLING

8.1.1 Lower Limit of Quantification (LLOQ) of E7777 Serum Concentration

The LLOQ of E7777 serum concentrations is 5.00 ng/mL

8.1.2 Below the Limit of Quantification (BLQ) Handling for Calculation of PK Parameters

While calculating PK parameters in WinNonlin, BLQ values will be handled according to 302-104.01-MNL, for non-compartmental pharmacokinetic analysis.

8.1.3 BLQ Handling for Developing Concentration-Time Profiles

When developing individual concentration-time profiles, BLQ values will be handled according to 302-104.01-MNL for non-compartmental pharmacokinetic analysis.

8.1.4 Handling of Anomalous Concentration Values

The handling of anomalous concentration values will follow the guidance in the SWP for non-compartmental pharmacokinetic analysis (302-104.01-MNL).

8.2.5 General Rules for Presentation of Drug Concentrations and PK Parameters

When presenting individual/raw (raw, hereafter) values and summary statistics, the following rule will be applied: for drug concentrations and concentration-dependent pharmacokinetic parameters, all summary statistics (mean, median, geometric mean, SD and CV) will have 3 significant digits. For t_{max} , raw values and their median are shown in fixed 2 decimal places.

Variable	Unit	N	Digit rule	Raw/ Minimum/	Mean Median	SD	Geometric Mean	CV (%)
				Maximum				
drug concentration	ng/mL	Х	Significant digits	3	3	3	-	-
C_{max}	ng/mL	Х	Significant digits	3	3	3	3	3
t_{max}	min	Х	Fixed decimal places	2	2	-	-	-
λ_z	1/min	Х	Significant	3				
κ_{z}	1/11111	Λ	digits	(Listing only)	-	-	-	-
t 1/2	min	Х	Significant digits	3	3	3	3	3
AUC(0-t),	ng•min/mL	Х	Significant	3	3	3	3	3
AUC (0-inf)	lig•iiiii/iiiL	Λ	digits	3	3	3	3	3
%AUC _{ex}	%	Х	Significant	3				
70AUCex	/0	Λ	digits	(Listing only)	-	-	-	-
MRT	min	Х	Significant digits	3	3	3	3	3
CL	mL/min/kg	Х	Significant digits	3	3	3	3	3
V_z, V_{ss}	mL/kg	Х	Significant digits	3	3	3	3	3
$R_{ac}(C_{max}),$ $R_{ac}(AUC)$		Х	Significant digits	3	3	3	3	3

Mean, SD, geometric mean and CV will not be calculated for $t_{\text{max}}.$

CV(%)= sqrt(exp[SD**2 of log transformed data]-1)*100

NOTE

- 1. The following parameters are reported in the CSR, but appear in Listings only. They are important information to confirm that individual t¹/₂ and its related parameters such as AUC_(0-inf) are appropriately derived and allow those PK parameters to be reproduced when necessary.
 - a. Time points used for estimation of terminal phase rate constant (λ_z) (lower and upper)
 - b. Number of the time points used for λ_z
 - c. Adjusted regression coefficient (R_{2adj})
 - d. Percentage of $AUC_{(0-inf)}$ obtained by extrapolation (%AUC_{ex})

In Listings, a) are shown in same digits as actual sampling time after dosing used for calculation of PK parameters. For b), integer number is used in Listings. For c) and d), significant 3 digits are used in Listing.

8.2 OTHER DATA HANDLING

Baseline

Baseline is defined as the last non-missing value observed prior to the first dose of study drug for a given parameter. For any Baseline value of 0, the subject's corresponding Percent Change from Baseline will not be included in the summary statistics tables.

Handling of Missing data

No imputation will be performed for missing data.

9 PROGRAMMING SPECIFICATIONS

The rules for programing derivations and dataset specification are provided as separate documents.

10 STATISTICAL SOFTWARE

PK Analysis will be performed using SAS for Windows (ver.9.2 or later), WinNonlin (Professional version 6.2.1 or later), Pharsight Knowledgebase Server (version 3.0 or later), Microsoft Excel (97 or later) and S-PLUS (6.1J or later for Windows).

Statistical analyses and summaries will be performed by Takumi Information Technology using SAS for Windows (ver.9.2 or later), and Microsoft Excel (2003 or later). Analyses will be conducted by using validated standard programs or double programming. For analyses needed in data review, single programming will be used.

11 MOCK TABLES, LISTINGS, AND GRAPHS

The study table, listing and graph shells will be provided in a separate document, which will show the content and format of all tables, listings, and graphs in detail.

13 APPENDICES

13.1 Table For Laboratory Result Grading Based on CTCAE version 4.03

This table is based on the CTCAE ver 4.03, but partially modified for the mathematical grading perpose.

	Common Terminolog	-	. ,	ersion 4.0						
Published: May 28, 2009 (v4.03: June 14, 2010) Grade										
Adverse event	1	2	3	4	5					
Blood and lymphatic system disorders										
Anemia	Hemoglobin (Hgb) <lln -="" 10.0="" dl;
<lln -="" 6.2="" l;
<lln -="" 100="" g="" l<="" td="">Hgb <10.0 - 8.0 g/dL; <6.2 - 4.9 mmol/L; <100 - 80g/L	Hgb <8.0 g/dL; <4.9 mmol/L; <80 g/L; transfusion indicated	Life-threatening consequences; urgent intervention indicated	Death	</lln></lln></lln>	Hgb <10.0 - 8.0 g/dL; <6.2 - 4.9 mmol/L; <100 - 80g/L	Hgb <8.0 g/dL; <4.9 mmol/L; <80 g/L; transfusion indicated	Life-threatening consequences; urgent intervention indicated	Death					
Leukocytosis	-	-	>100,000 /mm ³	Clinical manifestations of leucostasis; urgent intervention indicated	Death					
		Investigation	S							
Alanine aminotransferase increased	>ULN - 3.0 × ULN	>3.0 - 5.0 × ULN	>5.0 - 20.0 × ULN	>20.0 × ULN	-					
Alkaline phosphatase increased	>ULN - 2.5 × ULN	>2.5 - 5.0 × ULN	>5.0 - 20.0 × ULN	>20.0 × ULN	-					
Aspartate aminotransferase increased	>ULN - 3.0 × ULN	>3.0 - 5.0 × ULN	>5.0 - 20.0 × ULN	>20.0 × ULN	-					
Blood bilirubin increased	>ULN - 1.5 × ULN	>1.5 - 3.0 × ULN	>3.0 - 10.0 × ULN	>10.0 × ULN	-					
Cholesterol high	>ULN - 300 mg/dL; >ULN - 7.75 mmol/L	>300 - 400 mg/dL; >7.75 - 10.34 mmol/L	>400 - 500 mg/dL; >10.34 - 12.92 mmol/L	>500 mg/dL; >12.92 mmol/L	-					
CPK increased	>ULN-2.5×ULN	>2.5×ULN-5×ULN	>5×ULN-10×ULN	>10×ULN	-					
Creatinine increased	>1 - 1.5 × baseline; >ULN - 1.5 × ULN	>1.5 - 3.0 × baseline; >1.5 - 3.0 × ULN	>3.0 × baseline; >3.0 - 6.0 × ULN	>6.0 × ULN	-					
GGT increased	>ULN - 2.5 × ULN	>2.5 - 5.0 × ULN	>5.0 - 20.0 × ULN	>20.0 × ULN	-					
Hemoglobin increased	Increase in >0 - 2 gm/dL above ULN or above baseline	Increase in >2 - 4 gm/dL above ULN or above baseline	Increase in >4 gm/dL above ULN or above baseline	-	-					

2				////-3001-203	
	if baseline is above ULN	if baseline is above ULN	if baseline is above ULN		
Lipase increased	>ULN - 1.5 × ULN	>1.5 - 2.0 × ULN	>2.0 - 5.0 × ULN	>5.0 × ULN	-
Lymphocyte count decreased	<lln -="" 800="" mm3; <lln -="" 0.8="" 10e9
/L</lln></lln>	<800 - 500/mm³; <0.8 - 0.5 × 10e9 /L	<500 - 200/mm³; <0.5 - 0.2 × 10e9 /L	<200/mm ³ ; <0.2 × 10e9 /L	-
Lymphocyte count increased	-	>4,000 - 20,000/mm³	>20,000/mm ³	-	-
Neutrophil count decreased	<lln -
1,500/mm³; <lln 1.5="" td="" ×<="" –=""><1,500 - 1,000/mm³; <1.5 - 1.0 × 10e9	<1,000 - 500/mm³; <1.0 - 0.5 × 10e9	<500/mm³; <0.5 × 10e9 /L	-	</lln></lln>	<1,500 - 1,000/mm³; <1.5 - 1.0 × 10e9	<1,000 - 500/mm³; <1.0 - 0.5 × 10e9	<500/mm³; <0.5 × 10e9 /L	-
Platelet count decreased	10e9 /L <lln -
75,000/mm³; <lln -="" 75.0="" td="" ×<="">/L <75,000 - 50,000/mm³; <75.0 - 50.0 ×	/L <50,000 - 25,000/mm³; <50.0 - 25.0 ×	<25,000/mm³; <25.0 × 10e9 /L	-	</lln></lln>	/L <75,000 - 50,000/mm ³ ; <75.0 - 50.0 ×	/L <50,000 - 25,000/mm ³ ; <50.0 - 25.0 ×	<25,000/mm ³ ; <25.0 × 10e9 /L	-
Serum amylase increased	10e9 /L >ULN - 1.5 × ULN	10e9 /L >1.5 - 2.0 × ULN	10e9 /L >2.0 - 5.0 × ULN	>5.0 × ULN	-
White blood cell decreased	<lln -
3,000/mm³; <lln -="" 10e9
/L</lln></lln>	<3,000 - 2,000/mm ³ ; <3.0 - 2.0 × 10e9 /L	<2,000 — 1,000/mm³; <2.0 - 1.0 × 10e9 /L	<1,000/mm ³ ; <1.0 × 10e9 /L	-
	Me	tabolism and nutritio	n disorders		
Hypercalcemia	Corrected serum calcium of >ULN - 11.5	Corrected serum calcium of >11.5 - 12.5	Corrected serum calcium of >12.5 - 13.5	Corrected serum calcium of >13.5 mg/dL;	Death
	mg/dL; >ULN - 2.9 mmol/L; lonized calcium >ULN - 1.5 mmol/L	mg/dL; >2.9 - 3.1 mmol/L; lonized calcium >1.5 - 1.6 mmol/L; symptomatic	mg/dL; >3.1 - 3.4 mmol/L; lonized calcium >1.6 - 1.8 mmol/L; hospitalization indicated	>3.4 mmol/L; Ionized calcium >1.8 mmol/L; Iife-threatening consequences	
Hyperglycemia	Fasting glucose value >ULN - 160 mg/dL; Fasting glucose value >ULN - 8.9 mmol/L	Fasting glucose value >160 - 250 mg/dL; Fasting glucose value >8.9 - 13.9 mmol/L	>250 - 500 mg/dL; >13.9 - 27.8 mmol/L; hospitalization indicated	>500 mg/dL; >27.8 mmol/L; Lifethreatening consequences	Death
Hyperkalemia	>ULN - 5.5 mmol/L	>5.5 - 6.0 mmol/L	>6.0 - 7.0 mmol/L; hospitalization indicated	>7.0 mmol/L; life-threatening consequences	Death
Hypernatremia	>ULN - 150 mmol/L	>150 - 155 mmol/L	>155 - 160 mmol/L; hospitalization indicated	>160 mmol/L; life- threatening consequences	Death

			1	1	T
Hypertriglyceridemi a	150 mg/dL - 300 mg/dL; 1.71 mmol/L - 3.42 mmol/L	>300 mg/dL – 500 mg/dL; >3.42 mmol/L - 5.7 mmol/L	>500 mg/dL - 1000 mg/dL; >5.7 mmol/L - 11.4 mmol/L	>1000 mg/dL; >11.4 mmol/L; life-threatening consequences	Death
Hyperuricemia	-	>ULN - 10 mg/dL (0.59 mmol/L)	-	>10 mg/dL; >0.59 mmol/L; life- threatening consequences	Death
Hypoalbuminemia	<lln -="" 3="" dl;
<lln -="" 30="" g="" l<="" td=""><3 - 2 g/dL; <30 - 20 g/L	<2 g/dL; <20 g/L	Life-threatening consequences; urgent intervention indicated	Death	</lln></lln>	<3 - 2 g/dL; <30 - 20 g/L	<2 g/dL; <20 g/L	Life-threatening consequences; urgent intervention indicated	Death
Hypocalcemia	Corrected serum calcium of <lln -
8.0 mg/dL; <lln -="" 2.0="" l;
lonized calcium <lln -
1.0 mmol/L</lln></lln></lln>	Corrected serum calcium of <8.0 - 7.0 mg/dL; <2.0 - 1.75 mmol/L; lonized calcium <1.0 - 0.9 mmol/L; symptomatic	Corrected serum calcium of <7.0 - 6.0 mg/dL; <1.75 - 1.5 mmol/L; lonized calcium <0.9 - 0.8 mmol/L; Hospitalization indicated	Corrected serum calcium of <6.0 mg/dL; <1.5 mmol/L; lonized calcium <0.8 mmol/L; life-threatening consequences	Death
Hypoglycemia	<lln -="" 55="" dl;
<lln -="" 3.0
mmol/L</lln></lln>	<55 - 40 mg/dL; <3.0 - 2.2 mmol/L	<40 - 30 mg/dL; <2.2 - 1.7 mmol/L	<30 mg/dL; <1.7 mmol/L; lifethreatening consequences; seizures	Death
Hypokalemia	-	<lln -="" 3.0
mmol/L;</lln>	<3.0 - 2.5 mmol/L; hospitalization indicated	<2.5 mmol/L; life-threatening consequences	Death
Hyponatremia	<lln -="" 130
mmol/L</lln>	-	<130 - 120 mmol/L	<120 mmol/L; life-threatening consequences	Death
		Renal and urinary d	isorders	1	
Proteinuria	1+ proteinuria; urinary protein <1.0 g/24 hrs	Adults: 2+ proteinuria; urinary protein 1.0 - 3.4 g/24 hrs; Pediatric: urine P/C	Adults: urinary protein >=3.5 g/24 hrs; Pediatric: urine P/C >1.9	-	-

Protein/Creatinine		
) ratio 0.5 - 1.9

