5.6.3 Laboratory Values

Laboratory results will be summarized using Système International (SI) units, as appropriate.

For all quantitative parameters listed in protocol Section 9.5.1.5.4 Safety Assessments (Laboratory Measurements), the actual value and the change from baseline to each post baseline visit and final observation will be summarized by visit using descriptive statistics. Qualitative parameters listed in protocol Section 9.5.1.5.4 will be summarized using frequencies (number and percentage of subjects), and changes from baseline to each post baseline visit and final observation will be reported using shift tables. Percentages will be based on the number of subjects with both non-missing baseline and relevant post baseline results.

CTCAE ver.4.03 will be used to identify subjects with treatment-emergent markedly abnormal laboratory values (TEMAVs). TEMAV is defined as a post baseline value with an increase from baseline to a grade of 2 or higher. When displaying the incidence of TEMAVs, each subject will be counted once in the laboratory parameter high and in the laboratory parameter low categories, as applicable.

The measured values for quantitative data will be displayed over time using Box plot.

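### In Appendix 13.1 hypokalemia and hyperuricemia enter at Grade 2 at the normal limit, so any new slight deviation counts as markedly abnormal; dipstick protein above 2+ has no grade

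*SAP*

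**What the plan says.** SAP Section 5.6.3 names the grading source: "CTCAE ver.4.03 will be used to identify subjects with treatment-emergent markedly abnormal laboratory values (TEMAVs"). It then sets the rule: "TEMAV is defined as a post baseline value with an increase from baseline to a grade of 2 or higher". Appendix 13.1 holds the cut-offs and says of itself: "This table is based on the CTCAE ver 4.03, but partially modified for the mathematical grading perpose".

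The rows that matter in Appendix 13.1 are these:

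- **Hyperuricemia.** Grades 1 and 3 are dashes. Grade 2 is ">ULN - 10 mg/dL (0.59 mmol/L"), and Grade 4 is ">10 mg/dL; >0.59 mmol/L; life- threatening consequences".
- **Hypokalemia.** Grade 1 is a dash. Grade 2 runs from LLN down to 3.0 mmol/L, and Grade 3 is "<3.0 - 2.5 mmol/L; hospitalization indicated".
- **Hyperkalemia**, for contrast. Grade 1 is ">ULN - 5.5 mmol/L", and Grade 2 starts above 5.5 mmol/L.
- **Proteinuria.** Dipstick 1+ is in Grade 1, and Grade 2 begins "Adults: 2+ proteinuria". The adult criterion in Grade 3 is a 24-hour protein of 3.5 g or more, with no dipstick level.

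Section 5.6.3 also provides by-visit summaries and box plots for quantitative parameters, and frequencies and shift tables for qualitative ones. These do not depend on the TEMAV rule.

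**The concern.** A Grade 2 threshold separates marked from slight abnormality only where the first out-of-range band is Grade 1. For low potassium and high uric acid that band is already Grade 2, so the TEMAV count becomes a count of subjects with any new out-of-range value in that direction. The same ion is treated differently on its two sides: low potassium qualifies at the normal limit, high potassium only above 5.5 mmol/L.

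The dipstick gap works the other way. In a table meant for numeric grading, a change from negative to 2+ is a TEMAV, while a change from negative to something worse matches no cell.

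The trial has a single arm (Section 3.2), so no control group shows how many such flags arise by chance. A reader of the TEMAV table could take ordinary variation in potassium and uric acid for marked toxicity, and could miss the worst dipstick results.

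**Working it through.** The plan gives no figure for this point, so there is none to reproduce.

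**Step 1: count the rows.** In Appendix 13.1, 26 rows have a first band starting at LLN or ULN. In 24 that band is Grade 1. The two exceptions are hypokalemia and hyperuricemia. (Increased lymphocyte count also lacks a Grade 1, but its Grade 2 starts at a fixed 4,000/mm³, so it is not among the 26.)

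**Step 2: apply the rule.** A TEMAV needs a post-baseline grade that is above the baseline grade and at least 2. The SAP gives no normal limits, so a range was assumed: potassium LLN 3.3 to 3.6 mmol/L, uric acid ULN 6 to 8 mg/dL, sodium LLN 136 mmol/L. Baseline is normal throughout.

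| Post-baseline result | Grade | TEMAV |
|---|---|---|
| Potassium 0.1 mmol/L below LLN (every LLN tried) | 2 | yes |
| Potassium 2.9 mmol/L | 3 | yes |
| Potassium 2.4 mmol/L | 4 | yes |
| Uric acid 0.1 mg/dL above ULN (every ULN tried) | 2 | yes |
| Uric acid 10.1 mg/dL | 4 | yes |
| Sodium 1 mmol/L below LLN | 1 | no |
| Dipstick 1+ | 1 | no |
| Dipstick 2+ | 2 | yes |
| Dipstick 3+ or 4+, no 24-hour protein | none | no |

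A subject already at Grade 2 at baseline who stays there is not counted. That dipsticks of 3+ or 4+ are reported is an assumption.

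**Step 3: size of the chance effect.** Assume that 2.5% of values lie beyond the relevant limit with no drug effect, that baseline is normal, and that there are n post-baseline draws. Eight draws is one per cycle over the maximum of 8 cycles (Section 3.2), 16 is two per cycle, and 2 to 4 stands for early discontinuation. The 35 subjects come from Section 4.

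- Independent draws: P = 1 − 0.975ⁿ.
- Correlated draws: each value is normal with a shared subject effect b and within-subject correlation ρ. With p(b) = Φ((1.96 − √ρ·b)/√(1 − ρ)), P = 1 − E[p(b)ⁿ⁺¹]/E[p(b)]. The extra power of one is the normal baseline.

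| Draws n | Independent | × 35 | ρ = 0.7 | × 35 |
|---|---|---|---|---|
| 2 | 4.9% | 1.7 | 3.0% | 1.1 |
| 4 | 9.6% | 3.4 | 5.0% | 1.8 |
| 8 | 18.3% | 6.4 | 7.8% | 2.7 |
| 16 | 33.3% | 11.7 | 11.3% | 4.0 |

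Per analyte, this is about 1 to 3 of 35 subjects with 2 to 4 draws and about 3 to 12 of 35 with 8 to 16 draws.

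**Step 4: after the change.** If the first band is Grade 1, the two slight deviations in Step 2 move from TEMAV to not TEMAV. Potassium below 3.0 mmol/L and uric acid above 10 mg/dL remain TEMAVs. If the dipstick entry covers 2+ or higher, a change from negative to 3+ becomes a TEMAV.

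**The case against.** The strongest reply is that nothing is contradicted. Section 5.6.3 refers to Grade 2, the appendix defines Grade 2, and the two can be programmed together. The appendix discloses that it was modified, and Section 7 lists an update of the grading rules. The potassium and uric acid placement may therefore be a deliberate worst-case choice. That stands as far as intent goes: a reader might infer a transcription error or a misquoted grading standard, but the SAP alone cannot show either. What it does show is that no reason is given for these two rows and that the TEMAV rule was not adapted to them. The disclosure does not explain the dipstick gap.

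A second reply is that TEMAV never had one meaning across analytes. Hyponatremia has no Grade 2 and so enters at Grade 3, increased lymphocyte count enters at Grade 2, and creatinine can reach Grade 2 on a multiple of baseline. This is right. A reader might infer that these two rows alone spoil comparison between analytes, or that correcting them would restore it; neither follows.

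Third, Section 9 leaves derivation rules to separate documents, so the program may already handle high dipstick values. A 24-hour protein would be graded in any case, and the qualitative shift tables would show a 3+ if urine protein is a listed qualitative parameter. A reader might infer that severe proteinuria would go unreported; the documents do not support that. The gap is in the TEMAV count only.

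Fourth, the larger chance figures need many draws. Patients with relapsed or refractory disease may stop early, and they need not vary as a healthy reference population does. This also stands, and is why the range starts at 2 draws.

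**Conclusion.** The point holds in limited form. For low potassium and high uric acid, any new value beyond the normal limit meets the TEMAV definition, unlike the other 24 rows tied to a normal limit. As printed, a dipstick above 2+ with no 24-hour protein is ungraded while 2+ is a TEMAV.

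A reader might take this to mean that every low potassium or high uric acid value is Grade 2. It is not: potassium below 3.0 mmol/L is Grade 3 or 4, and uric acid above 10 mg/dL is Grade 4. The issue is where the lowest band sits.

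The chance flags, from about 1 to about 12 of 35 subjects per analyte, are an illustration and not an estimate for this trial, since neither the 2.5% tail nor the number of draws is in the SAP. The effect is confined to the descriptive TEMAV table. The primary endpoint, the sample size and the efficacy analyses are untouched. This is a minor correction.

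**What to change.** In Appendix 13.1, place the potassium band from LLN to 3.0 mmol/L and the uric acid band from ULN to 10 mg/dL in Grade 1. If the Grade 2 placement is deliberate, keep it, say so, and state in Section 5.6.3 that a TEMAV for these two analytes requires the next band. In the proteinuria row, change the Grade 2 dipstick entry to 2+ or higher.

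The work is three table entries, or a short statement and one entry, plus the matching lines of the grading program.

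The price is sensitivity. Under either option a potassium TEMAV would be Grade 3 or higher and a uric acid TEMAV only Grade 4, so fewer subjects are flagged and the two thresholds become strict. The by-visit summaries and box plots still show all values, so no data are lost from the report.
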